### **7.2.6 End of Study and Follow Up**

Participation ends with the participant's final study visit (either the in-person follow-up visit or telephone survey, for selected participants). Study staff will complete a study discontinuation/completion case report form for each participant, regardless of disposition. The form will track the off-study date, off-study reason, and reason for discontinuation for those who left the intervention prematurely (e.g., lost to follow-up, left the study area early).

### **7.2.7 Removal of Subjects**

Enrolled participants may withdraw from the study at any time for any reason upon request without penalty. A study discontinuation form will be completed as described in section 7.3.6.

An investigator may withdraw a participant from the study for the following reasons:

- If any clinical adverse event (AE), serious adverse event (SAE), or other medical condition or situation — related or unrelated to the study — develops after enrollment such that continued participation in the study would not be in the best interest of the participant.
- If a patient presents a safety risk to the research staff.
- If their participation in the study is disruptive to the study.

## **7.3 Statistical Method**

### **7.3.1 Statistical Design**

The pilot trial features a single-group, pre-post quasi-experimental design. As this is a feasibility study, hypothesis testing on the main effectiveness outcomes is strictly exploratory. Analysis assumes a null hypothesis of no participant-level change in the outcome measures from baseline to follow-up. Inferential analysis will be conducted on all outcome measures described in 7.1.3.

Basic descriptive statistics will be calculated for feasibility, acceptability, and outcome measures. We will present frequency tables for the categorical variables and means, standard deviations, and percentiles (25th, 50th, 75th) for the continuous variables. For outcome

measures, descriptive statistics will be calculated for baseline scores, follow-up scores, and change in scores.

Inferential analysis will be conducted on participant-level change in outcome measures from pre to post using paired t-tests (or Wilcoxon signed-ran tests if response distributions are non-normal). We will also examine differences in mean change scores across levels of each demographic variable using ANOVA. Significance levels for analyses will be set at  $\alpha=0.05$ . We will use R version 4.3.0 for data cleaning, management, and analysis.

### **7.3.2 Sample Size Considerations**

The proposed sample size is 30. As the primary goal is to assess feasibility and acceptability, not effectiveness, sample size is not based on anticipated effect sizes. Previous guidance has indicated our proposed sample size is an acceptable number for feasibility studies. This sample size will allow us to estimate the retention rate to within a 95% confidence interval of +/- 12% (calculated assuming a retention rate of 85%). Although exploratory only, the sample size will further allow us to detect moderate effect sizes in the continuous outcomes (Cohen's  $d = 0.53$ ) with 80% power (alpha = .05, two-tailed) using paired t-tests. Power calculations were performed using G\*Power 3.1.9.7.

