### Implementation Feasibility Measures

Measures indicating feasibility of implementation include recruitment rate (% screened who are deemed eligible, % screened who proceed to consent and enrollment), retention rate (% enrolled who complete post-survey), time from recruitment initiation to sample saturation, and intervention engagement (message response rate and mean response time).

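### The stated retention precision of ±12% should be about ±13%: 30 participants at 85% retention give a half-width of 12.8 points

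*Combined protocol and SAP*

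**What the plan says.** Section 7.3.2 (Sample Size Considerations) fixes the number of participants: "The proposed sample size is 30". It then gives the precision this buys for one feasibility outcome, which is to "estimate the retention rate to within a 95% confidence interval of +/- 12% (calculated assuming a retention rate of 85"%). The same statement appears in 6.1.1 (Number of Participants) and in the Synopsis under the same heading.

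The Implementation Feasibility Measures in 7.1.3 define the outcome as "retention rate (% enrolled who complete post-survey"). The Synopsis and 5.2.1 define it in the same way. The denominator is therefore everyone enrolled, that is, 30.

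No interval method is named for the retention figure. Section 7.3.2 does name software, but only for power: "Power calculations were performed using G\*Power 3.1.9.7".

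**The concern.** The sentence gives every input needed to check it: the sample size, the assumed rate and the confidence level. The standard formula applied to them does not return 12. The printed margin is narrower than the inputs support, so the plan claims slightly more precision than it has.

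This is the only precision figure given for any feasibility outcome, and the plan describes feasibility and acceptability as its main goal. The accompanying power statement is labelled exploratory. A sentence that appears three times could also be carried into the manuscript planned in 8.15, where a reader can check it in one line.

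**Working it through.** **Inputs**

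- n = 30 (7.3.2, 6.1.1, Synopsis), which is also the denominator because retention is a share of those enrolled (7.1.3).
- p = 0.85, the assumed retention (same three places).
- 95% confidence, read as two-sided because the margin is written as ±; z = 1.96.
- Stated half-width: 12 points.

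**Attempt to reproduce the plan's figure**

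Normal-approximation (Wald) half-width = z × √(p(1 − p)/n).

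- p(1 − p) = 0.85 × 0.15 = 0.1275
- 0.1275 / 30 = 0.00425, with square root 0.0652
- 1.96 × 0.0652 = 0.1278, or 12.8 points

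The interval is 85 ± 12.8, or 72.2% to 97.8%. The printed margin implies 73% to 97%. To the nearest whole percent the half-width is 13, so the stated figure is not reproduced.

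**Does another method give 12?** Half-widths at p = 0.85 and n = 30, as half the interval's total width:

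| Method | Half-width (points) |
|---|---|
| Arcsine | 12.51 |
| Jeffreys, equal-tailed | 12.54 |
| Wilson | 12.7 |
| Wald | 12.8 |
| Wald with n − 1 | 13.0 |
| Wald with z = 2 | 13.0 |
| Agresti-Coull | 13.2 |
| Logit | 13.2 |
| Wald with t quantile | 13.3 |
| Exact (Clopper-Pearson, fractional count 25.5) | 14.0 |
| Wald with continuity correction | 14.4 |

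All round to 13 or more. A one-sided 95% bound gives 10.7, which does not match either.

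**What would give 12?** 85% of 30 is 25.5 people, so a whole-person calculation would use a neighbouring count:

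- 26/30 = 86.7%: 1.96 × √(0.8667 × 0.1333 / 30) = 12.2 points
- 25/30 = 83.3%: 1.96 × √(0.8333 × 0.1667 / 30) = 13.3 points

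With n = 30, a Wald half-width that rounds to 12 needs retention of at least about 85.8%. At 85%, n = 31 gives 12.6 and n = 32 gives 12.4, so rounding to 12 needs n = 32. A half-width of 12.0 needs 1.96² × 0.1275 / 0.12² = 34.0, or about 34 participants.

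**Cross-check on the adjacent claim.** A two-sided paired t-test with d = 0.53, n = 30 and α = 0.05 has power 0.801. The power statement in the same paragraph therefore does reproduce at n = 30.

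**The case against.** The strongest objection is that the error does not matter. The gap is 0.8 of a point, and intervals of 73–97% and 72–98% would lead any reader to the same judgement. The plan rests n = 30 first on cited guidance, no progression threshold uses the margin, feasibility is to be reported descriptively, and no confidence interval for retention is planned. All of that stands. It limits the importance of the point but does not make the figure right.

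A second objection is that 12 can be reached. Exactly 85% cannot occur among 30 people, and 26/30 gives 12.2. This may explain how the number arose, but the text states 85%, so one of the two printed numbers would still be wrong.

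A third is that no method is named, and highest-density credible intervals at 85% and n = 30 have half-widths of 12.2 (Jeffreys prior) and 12.4 (uniform prior). These do round to 12, so it would be too strong to say that no interval of any kind could. But they are asymmetric credible intervals, the plan describes a symmetric confidence interval, and nothing in it suggests a Bayesian calculation.

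Finally, advice on the choice of interval method goes beyond correcting the arithmetic. That is fair, and it is kept separate below as optional.

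**Conclusion.** The figure is wrong as written. With 30 enrolled participants and 85% retention, the two-sided 95% normal-approximation half-width is 12.8 points, or about ±13%. The stated ±12% is too favourable by 0.8 of a point. Whether 12.78 was truncated or 26/30 was used cannot be determined from the documents.

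The conclusion assumes the normal approximation, which a symmetric margin implies. It does not hang on that choice: none of the confidence-interval methods tabulated above rounds to 12 at these inputs. The point is minor. It does not affect the sample size, conduct or analysis of the trial.

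**What to change.** Keep n = 30. In 7.3.2, 6.1.1 and the Synopsis, change the margin to about ±13% and say that it is a normal approximation assuming 85% retention. If the calculation was in fact made for 26 of 30, keep 12% and replace 85% with 86.7% (26/30).

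The cost is one figure in three places. The stated precision becomes slightly less favourable and nothing else changes.

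Optional, and separate from the correction: a symmetric margin understates the downside at a rate this high. Wilson limits at 85% are 68% to 94%, about 17 points below and 9 above; exact limits for 26/30 are 69% to 96%, about 17 below and 10 above. The team could quote one such interval in the plan and use the same method when reporting observed retention.

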After consent is obtained, participants will complete a computer-assisted self-interview (CASI) baseline survey hosted on Qualtrics, a secure HIPAA-compliant platform. Participants will then be given a brief oral orientation to the intervention.

Participants will be considered enrolled upon meeting eligibility criteria, signing the consent form, completing the baseline CASI survey, and successfully enrolling in the text messaging program on their phones.

Retention. We will collect multiple forms of participant contact information and study-related communication preferences (e.g. email, phone/text, social media handles) as part of study enrollment. Using a participant locator form at the baseline visit, participants will indicate which forms of contact they prefer if they cannot be reached on their primary phone. If the participant consents for a friend or family member to be contacted for follow-up, no details of the study will be shared, only that the participant is being contacted about a health study.

Likelihood of recruitment success. There is a high likelihood that we will have access to the anticipated sample size (n=30). Our study team has successfully met recruitment quotas across several quantitative and qualitative research projects in southern Ohio over the past 6 years, including formative qualitative interviews for the current study (n=22), which were completed in 3 weeks in October 2023. The primary recruitment site, SHRPS, is frequently utilized for harm reduction services by people who use drugs. In 2021, SHRPS had 2,199 unique visitors and 12,111 interactions. The program is operated by the Portsmouth Health Department three days a week. The SSP has served as a recruitment site for more than four years in the parent study. SHRPS is well-situated for recruitment given the trust, safety, and legitimacy it has cultivated with the local PWUD community.

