### **7.3.3 Planned Analyses**

#### **7.3.3.1 Primary Analyses**

The primary outcomes (stigma resistance and self-stigma) and secondary outcomes (hope and self-esteem) will each be measured at baseline and follow-up for all participants. The effectiveness of the intervention will be measured as the mean change in participant-level outcome scores from pre to post given the null hypothesis of no change and a type I error rate of 0.05. We will use an intention-to-treat approach, including all participants with complete pre and post data in analysis regardless of adherence.

Feasibility and acceptability will be characterized descriptively, as described in 7.4.1.

Follow-up telephone interviews will be transcribed and computerized for analysis in the qualitative data analysis program Dedoose (v9.0). Transcripts will be coded and analyzed for emerging themes on intervention acceptability using the Braun & Clarke (2006) approach to reflexive thematic analysis (TA).

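### The stated 80% power at d = 0.53 needs all 30 enrolled participants to have both surveys, but the plan assumes 85% retention and tests only complete pairs

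*Combined protocol and SAP*

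**What the plan says.** Section 7.3.2 opens with "The proposed sample size is 30" and explains that this number rests on feasibility, not on an expected effect size. It then makes two quantitative claims in consecutive sentences.

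- The first concerns the precision of the retention rate, "calculated assuming a retention rate of 85" per cent.
- The second is that "the sample size will further allow us to detect moderate effect sizes in the continuous outcomes", quantified as Cohen's d = 0.53 "with 80% power (alpha = .05, two-tailed) using paired t-tests". It is introduced as exploratory, and G*Power is named as the software.

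The same two claims stand in the Synopsis (Number of Participants) and in Section 6.1.1.

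Three other places fix how many pairs the test will have.

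- Section 7.1.3 (Implementation Feasibility Measures) defines retention as the share of enrolled participants who complete the follow-up survey.
- Section 7.2.4 makes enrolment conditional on, among other things, "completing the baseline CASI survey, and successfully enrolling in the text messaging program on their phones". Everyone counted as enrolled therefore already has a baseline survey.
- Section 7.3.3.1 describes the analysis as intention-to-treat, "including all participants with complete pre and post data in analysis regardless of adherence".

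Section 7.3.4 adds multiple imputation, but only if the review of missing data suggests bias.

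**The concern.** A paired t-test uses only people measured twice, so its power depends on the number of complete pairs and not on the number enrolled. The power sentence appears to treat all 30 enrolled as pairs, which implies 100% follow-up, while the sentence before it plans for 85%. The two sentences share one sample size but use different retention rates, and the analysis rule in Section 7.3.3.1 agrees with the lower one.

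What is at stake is how the result is read. Section 5.1 names the changes in stigma resistance and self-stigma as the primary outcomes, Section 7.3.3.1 tests them at 0.05, and Section 5.2.1 links later trials partly to preliminary effectiveness. A reader facing a non-significant change would take it that the study had an 80% chance of detecting 0.53, when the plan's own assumptions give a lower chance.

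A smaller point is that the text does not say which d it means. For a paired t-test it is the mean change divided by the SD of the change scores, which is not the same scale as an effect expressed in raw-score SDs.

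**Working it through.** **Inputs**

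- Enrolled: 30 (Section 7.3.2).
- d = 0.53, power 80%, two-sided alpha 0.05, paired t-test (Section 7.3.2).
- Retention: 85% (Section 7.3.2), the only retention assumption in the documents.
- Pairs = enrolled × retention, because every enrolled participant has baseline data (Section 7.2.4) and retention counts follow-up surveys (Section 7.1.3).
- Allowance for loss: none. The 40 in Section 6.1.1 is the number to be screened in order to reach 30.

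**Formula**

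For n pairs, df = n − 1 and the noncentrality parameter is d × √n. Power is the probability that a noncentral t variable with these parameters falls outside ± the 97.5th percentile of the central t distribution with the same df.

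**Step 1: reproduce the stated figure**

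With n = 30, the noncentrality is 0.53 × √30 = 2.90 on 29 df. Power is 80.1%, and the d detectable with 80% power is 0.529. The plan's figure is therefore correct for 30 complete pairs. Other readings at n = 30 fit less well: a normal approximation gives 82.7% and a one-sided test 88.3%. There is no slack, because 30 is the smallest number of pairs that reaches 80% at d = 0.53, and 29 pairs give 78.7%.

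**Step 2: apply the plan's own retention**

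30 × 0.85 = 25.5 expected pairs.

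| Complete pairs | Power at d = 0.53 | d detectable with 80% power |
|---|---|---|
| 30 | 80.1% | 0.529 |
| 29 | 78.7% | 0.539 |
| 26 | 73.8% | 0.572 |
| 25.5 | 72.9% | 0.578 |
| 25 | 72.0% | 0.584 |

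Averaging over a Binomial(30, 0.85) number of completers, instead of fixing it at its mean, gives 72.7%. If each person is retained independently with probability 0.85, the chance that all 30 return is 0.85^30, about 0.8%.

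**Step 3: the shortfall**

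Against the stated 80%, power is 80 − 73.8 = 6.2 to 80 − 72.0 = 8.0 points lower. Against the stated 0.53, the detectable d is 0.572 − 0.53 = 0.04 to 0.584 − 0.53 = 0.05 higher.

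If the Wilcoxon alternative in Section 7.3.1 is used, power at 25 to 26 pairs is about 70% to 72%. This approximation takes the asymptotic relative efficiency under normality, 3/π.

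**Step 4: the scale of d**

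If baseline and follow-up have equal SDs and correlation r, a paired d of 0.53 equals 0.53 × √(2(1 − r)) raw-score SDs. The documents give no r. For assumed values of 0.3, 0.5 and 0.7 the result is 0.63, 0.53 and 0.41.

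**The case against.** The strongest reply is that nothing depends on this number. Section 7.3.2 labels the power statement exploratory and says the sample size does not rest on effect sizes. Section 4.1 says there is no formal hypothesis testing, and Section 7.3.1 calls the tests strictly exploratory. No progression rule uses the p-value, and a detectable d of 0.57 to 0.58 can still be called moderate. All of this stands and limits the importance of the point. It does not make the figure right: the plan gives an effect size, a power and an alpha in three places, and plans that test on outcomes it calls primary.

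A second reply is that the software output is correct and the 85% belongs only to the precision sentence. It is true that there is no slip in the calculation; the fault is an unstated assumption of complete follow-up. But 85% is the plan's only expectation for the quantity that sets the number of pairs, and no reason is given for using a different value one sentence later.

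A third is that multiple imputation could bring all 30 back into the analysis. Section 7.3.4 makes imputation conditional on suspected bias and names no imputation model or auxiliary variables, and the power statement does not rely on it. It cannot be counted on to restore the information in 30 observed pairs.

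The remark on the definition of d can also be called minor, since naming a paired t-test and G*Power lets a careful reader work it out. That is fair. It merits a few words in the correction and no more.

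**Conclusion.** The concern holds. The stated 80% power at d = 0.53 is right for 30 complete pairs and wrong for the analysis the plan expects to run. At the assumed 85% retention, power at 0.53 is about 73%, and 80% power is reached at a d of about 0.58.

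This rests on three things: 85% is the expected retention, the analysis uses observed pre-post pairs, and change scores are close enough to normal for the t-test calculation. If retention were complete the stated figure would stand, but losing even one participant takes power below 80%. The error affects how the preliminary effectiveness results are interpreted. It does not affect the feasibility and acceptability aims or the justification for enrolling 30.

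**What to change.** Keep 30 participants and replace the power sentence in the Synopsis (Number of Participants), Section 6.1.1 and Section 7.3.2 with wording such as:

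> With 30 enrolled and 85% retention (25 to 26 participants with both surveys), a two-sided paired t-test at 0.05 has 80% power for a standardised mean change (mean change divided by the SD of change) of about 0.58. Power for 0.53 is about 73%. This calculation is exploratory and does not determine the sample size.

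The cost is one sentence in three places and a slightly less favourable figure.

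The alternative is to keep the claim as it stands and enrol enough people to expect 30 pairs: 30 / 0.85 = 35.3, so 36. As the sample size was chosen for feasibility, restating the figure is the proportionate choice.

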### **7.3.3 Planned Analyses**

#### **7.3.3.1 Primary Analyses**

The primary outcomes (stigma resistance and self-stigma) and secondary outcomes (hope and self-esteem) will each be measured at baseline and follow-up for all participants. The effectiveness of the intervention will be measured as the mean change in participant-level outcome scores from pre to post given the null hypothesis of no change and a type I error rate of 0.05. We will use an intention-to-treat approach, including all participants with complete pre and post data in analysis regardless of adherence.

Feasibility and acceptability will be characterized descriptively, as described in 7.4.1.

Follow-up telephone interviews will be transcribed and computerized for analysis in the qualitative data analysis program Dedoose (v9.0). Transcripts will be coded and analyzed for emerging themes on intervention acceptability using the Braun & Clarke (2006) approach to reflexive thematic analysis (TA).

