### **3.3 Potential Risks and Benefits**

#### **3.3.1 Potential Risks**

Emotional distress. A small risk of psychological distress (e.g., embarrassment, upset) is posed by study questions concerning stigma. Participants may find answering questions about these issues upsetting; participants will be reminded at the beginning of the pre- and post-surveys that they may decline to answer any questions at any time without any repercussions. Survey administrators will be trained to recognize the signs of distress and how to respond appropriately, including expressing empathy and offering to pause or end the survey with no repercussions to the participant. In our experience using similar data collection methods in the past with people who use drugs, the likelihood and seriousness of this risk is minimal, and we will strive to create a safe and comfortable environment for all study participants.

A secondary source of psychological risk is during administration of the intervention. Though the text message content is positive and affirming, mention of stigma may distress some participants. During the intervention orientation, participants will be provided a list of external counseling and support resources they can access if they feel distressed. These resources will also be shared in a text message during the intervention, along with a text message that the messaging exchange will not be monitored and participants should reach out to the suggested resources if they feel distressed.

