#### 7.1.3 Selection of Instruments/Outcome Measures

##### Preliminary Effectiveness Outcome Measures

Preliminary effectiveness outcome measures were selected based on construct validity to the outcomes and internal consistency reliability.

Construct	Measure	Example Question
-----------	---------	------------------

Stigma resistance	Stigma Resistance Scale (Firmin, Lysaker, et al., 2017) 20 items, Likert-type, $\alpha=.93$	"I challenge negative thoughts that I may have about myself related to my substance use."
Self-stigma	Substance Abuse Self-Stigma Scale (Luoma et al., 2013) 40 items, Likert-type, $\alpha=.86$	"I feel inferior to people who have never had a problem with substances."
Hope	Adult Dispositional Hope Scale (Snyder et al., 1991) 12 items, Likert-type, $\alpha=.77-.84$	"Even when others get discouraged, I know I can find a way to solve the problem."
Self-esteem	Rosenberg Self-Esteem Scale (Rosenberg, 1965) 10 items, Likert-type, $\alpha=.77$	"I feel I do not have much to be proud of."
Covariates	Age, race, gender, educational attainment, drug of choice (all categorical)	N/A

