#### **7.3.4 Handling of Missing Data**

To address missing data, we will review the frequency of missing and non-missing values for all variables at baseline and follow-up. We will conduct missing value analyses to determine whether persons with missing values are systematically different from those without missing values. If this assessment of the frequency of missing data suggests that bias may be introduced, we will employ multiple imputation to address the missing data.

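### The effectiveness analysis is labelled intention-to-treat but is a complete-case analysis; the power figure assumes no dropout, and the imputation step has no operational trigger or stated rank

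*Combined protocol and SAP*

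**What the plan says.** Section 7.3.3.1 sets the population for the mean change in each outcome: "We will use an intention-to-treat approach, including all participants with complete pre and post data in analysis regardless of adherence".

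Two definitions elsewhere decide who that leaves out. Section 7.2.4: "Participants will be considered enrolled upon meeting eligibility criteria, signing the consent form, completing the baseline CASI survey" and being signed up to the messaging program. Section 7.1.3, under Implementation Feasibility Measures, lists as an outcome "retention rate (% enrolled who complete post-survey").

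Section 7.3.2 gives a detectable effect of d = 0.53 for a sample of 30, "with 80% power (alpha = .05, two-tailed) using paired t-tests". The same section assumes 85% retention when it works out the precision of the retention rate.

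Section 7.3.4 plans a review of how often values are missing and of whether people with missing values differ from those without. It then says: "If this assessment of the frequency of missing data suggests that bias may be introduced, we will employ multiple imputation". It names no test, threshold or imputation model, and it does not rank the imputed result against the one in 7.3.3.1.

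Section 7.3.1 supplies the lead test (paired t-test, or Wilcoxon signed-rank if distributions are non-normal) and calls testing on effectiveness strictly exploratory.

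**The concern.** The 7.3.3.1 sentence combines a label with a rule that contradicts it. Analysing people regardless of adherence is one element of intention-to-treat. Dropping enrolled people because they have no follow-up breaks the other. Change in stigma resistance and self-stigma is the named primary outcome (sections 5.1 and 7.3.3.1), and section 8.15 says that primary results, with any appropriate tests, will be posted publicly. A reader told that the result is intention-to-treat would take it to cover everyone enrolled.

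Two consequences follow. The power statement in 7.3.2 describes a set larger than the one to be analysed. And because the imputation step is left to a judgement with no stated rank, two analysts could both follow the plan and put forward different results once follow-up data are missing.

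**Working it through.** **1. Who is in the set.** Everyone enrolled has completed the baseline survey (7.2.4). Everyone not retained has no post-survey (7.1.3). Complete pre and post data therefore excludes all non-returners.
- At 85% retention, 30 × 0.85 = 25.5 remain, so 4 to 5 of 30 are left out.
- Over the plan's own 85% ± 12% (73% to 97%), 30 × 0.03 = 0.9 to 30 × 0.27 = 8.1, or about 1 to 8 of 30, are left out.

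**2. The plan's power figure.** Paired t-test, two-sided α = 0.05, noncentral t with df = n − 1 and noncentrality d√n.
- n = 30, d = 0.53: 0.53 × √30 = 2.90, critical t = 2.045, power 80.1%. The detectable d at 80% power is 0.529. The stated figure is reproduced, but only with 30 complete pairs.

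**3. The same formula on the set in 7.3.3.1.**

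| Pairs | d√n at 0.53 | Power at d = 0.53 | d at 80% power |
|---|---|---|---|
| 30 | 2.90 | 80.1% | 0.529 |
| 26 | 2.70 | 73.8% | 0.572 |
| 25 | 2.65 | 72.0% | 0.584 |

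**4. What the missingness review could show.** Section 7.3.4 names no test, so assume a two-sided 5% t-test on a baseline score, returners against non-returners. The noncentrality is δ√(n₁n₂/(n₁+n₂)) with 28 df.
- 25 v 5: δ = 0.5 SD gives 0.5 × √(125/30) = 1.02, power 17%; δ = 0.8 SD gives 35%.
- 26 v 4: δ = 0.5 SD gives 0.5 × √(104/30) = 0.93, power 15%; δ = 0.8 SD gives 30%.

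No comparison of observed values can show dropout that depends on the follow-up score that was not collected.

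**5. Likely size of bias.** Simulation with assumed inputs: n = 30, 85% retention, true change −0.40 SD, pre-post correlation 0.5, logistic dropout with slope 0.75 or 1.2 per SD, 20,000 replicates. The trigger is the t-test of step 4. The all-enrolled estimate is a regression on baseline, standing in for multiple imputation.

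| Dropout more likely with | Completers | All enrolled | Trigger fires |
|---|---|---|---|
| Higher baseline score | −0.348 / −0.325 | −0.401 / −0.402 | 26% / 51% |
| Higher follow-up score | −0.453 / −0.478 | −0.480 / −0.519 | 10% / 15% |

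Completer bias is 0.05-0.08 SD, in either direction, against a standard error of about 0.20. With dropout on baseline, 95% interval coverage is 94.3% or 93.5%. In the second row the trigger fires least often, and the all-enrolled estimate is further from the truth than completers (RMSE 0.210-0.226 against 0.205-0.209).

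**The case against.** The best defence is that this is a single-arm feasibility study in which little turns on the effectiveness result. Section 7.3.1 calls the testing strictly exploratory, section 4.1 says outcomes are presented descriptively, and section 7.3.2 says the sample size does not rest on an effect size. Retention is itself an outcome, off-study reasons are recorded (7.2.6), and participant flow will be reported (8.15). The simulated bias is well inside one standard error. All of that stands, and it limits the severity. It does not make the label true, and a flow table does not rank two analyses.

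Stronger readings are tempting and should be resisted:

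- A reader might infer that the lead set cannot be identified. At participant level it can: 7.3.3.1 describes it under Primary Analyses and 7.3.1 gives the tests. What is open is the standing of an imputed result once one is triggered.
- A reader might infer that imputation has no criterion at all. Section 7.3.4 gives a qualitative one; what is missing is an operational one.
- A reader might infer that skipped items will shrink the set sharply, because participants are told that "they may decline to answer any questions at any time without any repercussions" and the self-stigma scale has "40 items, Likert-type". The documents give no skip rate, and sections 7.2.4 and 7.1.3 speak of completion at survey level. The absence of a scoring rule is missing detail, and no loss can be put on it.
- The firing rates and the 15-35% powers belong to a t-test that this review assumed, not one that the plan names.

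**Conclusion.** The point holds in a limited form and should be fixed. The intention-to-treat label is wrong on the plan's own definitions, and this needs no assumption. The power figure is correct for 30 pairs but does not describe the planned set: at the plan's 85% retention it is 72-74% at d = 0.53, or d = 0.58-0.57 at 80% power. The imputation trigger is a judgement, likely to rest on comparing 25-26 people with 4-5, and the rank of its result is unstated.

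The documents do not support a claim that the effectiveness estimate will be seriously wrong. Under the assumed dropout models the bias at 85% retention is 0.05-0.08 SD and its direction is unknown. The reason to act is that a stated property is false and a choice is left open.

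**What to change.** 1. **Section 7.3.3.1.** Replace the intention-to-treat wording with: complete-case (available pairs) analysis, regardless of adherence. Keep the paired t-test or Wilcoxon test on this set as the lead analysis, and report for each outcome the number contributing out of those enrolled.
2. **Section 7.3.2.** State that d = 0.53 assumes 30 complete pairs, and add d = 0.57-0.58 at 80% power (or 72-74% power at 0.53) for the expected 25-26 pairs. No change in enrolment is needed.
3. **Section 7.3.4.** Drop the judgement-based trigger. Whenever follow-up scores are missing, report a multiple-imputation analysis of all enrolled participants, with its model named, beside the lead result as a sensitivity analysis.

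Optional: a scoring rule for skipped items, and a range of shifts applied to the imputed follow-up scores. For a 30-person pilot these are matters of preference.

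The cost is a few sentences and a little extra R code, with no new data and no change to the lead tests. The downside is that imputation assuming missing at random can be further off than completers if dropout depends on the follow-up score (second row of the simulation). That is why it should stay a sensitivity analysis.
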